A further assessment of the BEA value cut off level will be made to see if a change in the standard definition is worth recommending (ROC analysis). This will be done at 18m from the start of the study (using cases accrued in the first year) and repeated on the new cases post 1 year recruitment to see if a new cut off level works on the second data group. The final sensitivity and specificity analysis will take place 6 months after the last case is recruited.

Analysis 2: Analysis of the sensitivity and specificity of the 18 month BEA assessment status (lymphoedema or not) against the 'gold standard' 18 month perometer assessment status (lymphoedema or not) using all data available at 18 months.

This analysis uses all the data available at 18 months, following the same logic and procedures as Analysis 1. Assuming at least 1,000 women are followed-up to 18 months after surgery, there will be more lymphoedema cases, this is estimated to be 35% of the total group (i.e. 350 cases). The sensitivity calculations produce a 95% CI for a 95% BEA sensitivity rate (333/350) against the perometer status at 18 months of 92.34 to 97.15 (again using the 'exact' method). The other 650 cases are used for the specificity calculation, here the 95% CI for 95% BEA specificity (618/650) has a 95% CI of 93.12 to 96.61. Consequently if sensitivity is <92% or specificity is <93% we can conclude that the true BEA rates are not as high as 95%.

Analysis 3: Assessment of the relationship between perometer measurement and BEA measurement. Any changes will be measured by both systems at different time points (1m, 3m, 6m, 12m and 18m and later on out to 5 years) and all results will be used as the modelling will be based on the paired perometer and BEA values. This will be used to define the relationship between the two methods (we will use Bland-Altman methods^{136,371} at individual time points and generalized estimating equations (GEE) regression models across time points). The relationship established may lead to a clearer definition of 'true' lymphoedema status when using either system.

Analysis 4: Cox regression multivariate analysis of the time to Lymphoedema (as defined by perometer) to find out what combination of variables gives the best prediction of these events.

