For this 'modelling' analysis we will use 'time to the first lymphoedema event per case' as the measure (cases not becoming lymphoedema will be censored at their last assessment time) and apply a Cox regression multivariate analysis to see what variables (if any) predict the long term outcome. The variables listed below are candidates. Concerns about the treatment paradox affecting this analysis will be dealt with by excluding cases who develop lymphoedema before 6 months and using a factor 'sleeve' v 'no sleeve' in the model to adjust for the cases treated in PLACE.

BMI, dominant limb, postoperative radiotherapy, previous sentinel node biopsy, cigarette smoking, weight gain, and age. As we will be measuring the patient's assessment of their own status using FACT-B and the Lymphoedema Symptom Checklist we will also use individual question responses and the overall scores for these questionnaires out to 6 months. The BEA values and perometer values are available at baseline, 3 months and 6 months. The 3 months and 6 months values will be used as distinct time points or as summary scores over the 3 measurements. It may well be possible to have a factor that represents 'early treatment' or 'lymphoedema status before 6 months', in which case all the information will be used. These variables will be assessed univariately and then as part of a multivariate model to see if any predict lymphoedema status by 18 months follow up.

As routine clinical data on lymphoedema status will be available in due course with 5 year follow up, a subsequent analysis will be possible to build a predictive model of outcomes up to 5 years.

This analysis will take place 18 months after the last case is entered. For the multivariate regression analyses, it is typically recommended that between 10 and 30 cases per variable are used. The higher number of cases per variable are required when the relationships are weaker. With approximately 1000 cases this should allow us to examine around 30 variables with at least sufficient power to pick up moderately weak relationships. See analysis 4 for the type of variables we will be assessing.

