- Group C: Women who develop greater than 10% arm swelling by 6 months (approximately 210 patients). Arm swelling of greater than 10% at 1 month will need confirmation but in current practice, we would review these patients at 3 months, before deciding to put on an arm sleeve as some women do observe amelioration of swelling over this period following the operation. Thus we will have 3 month perometer readings on all patients in this group to compare with 3 month BEA measurements. All other patients will provide 6 month perometer and BEA measurements and will therefore be eligible for the analysis of the prediction of arm swelling at 18 and 36 months. The data for patients who have undergone treatment before 6 months in this group will not be included in our multivariate analysis, although we expect few cases to be excluded in this way.

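### The claim that about 1000 cases support around 30 predictors in the Cox model counts women, not lymphoedema events, and no event count in the protocol supports it at the level stated for weaker relationships

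*Protocol*

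**What the plan says.** Analysis 4 in section 5 is a Cox regression of time to first lymphoedema by perometer. Women who do not develop it are censored at their last assessment. On model size the protocol says "it is typically recommended that between 10 and 30 cases per variable are used", adds that "The higher number of cases per variable are required when the relationships are weaker", and concludes: "With approximately 1000 cases this should allow us to examine around 30 variables with at least sufficient power to pick up moderately weak relationships".

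The expected events are given elsewhere in section 5. Analysis 2 begins "Assuming at least 1,000 women are followed-up to 18 months after surgery" and says of the lymphoedema cases that "this is estimated to be 35% of the total group (i.e. 350 cases"). Group C is described as "Women who develop greater than 10% arm swelling by 6 months (approximately 210 patients").

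The protocol gives three rules for early cases in this model:

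- Analysis 4 handles the treatment paradox by "excluding cases who develop lymphoedema before 6 months and using a factor 'sleeve' v 'no sleeve' in the model".
- Analysis 4 then says a factor for early treatment or early lymphoedema may be possible, so that no information is lost.
- The text around Groups A to C drops women treated before 6 months. Of these, the Group C paragraph says "although we expect few cases to be excluded in this way".

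**The concern.** A rule of so many cases per variable is a rule about information. In a time-to-event model with censoring, a woman who never has the event adds far less information than one who does, so the rule has to be read as events per variable. Applied to women, it overstates the size of model the data can carry.

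The candidate list makes this matter. It has seven clinical factors, individual questionnaire responses (section 8 gives FACT-B+4 forty items), a symptom checklist, perometer and BEA values at several visits, and a sleeve factor. The first two groups alone give 7 + 40 = 47 candidates.

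The model serves secondary objective 4, and section 2.0 plans to combine it with PLACE data in an economic model. Overfitted coefficients would carry into the cost-effectiveness results. If early cases are removed, the estimates describe only later-onset lymphoedema.

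**Working it through.** **1. The plan's own figure.** 1000 women / 30 per variable = 33.3, which rounds to around 30. Using only the women left after removing 210 gives 790 / 30 = 26.3, again about 30. Both counts are of women. The 30-per-variable end is also the end the protocol ties to weaker relationships.

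**2. Events needed for 30 variables.** At 10 each: 30 × 10 = 300. At 30 each: 30 × 30 = 900.

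**3. Events available, per 1000 women unless stated.** Inputs:

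- 35% with lymphoedema at 18 months (section 5, Analysis 2)
- 21% by 6 months: 210 per 1000 (Group C), or 231 of 1100 (Analysis 1)
- 5% already at a 10% increase at 3 or 6 months, and up to 40% of women with moderate early swelling not progressing by 2 years (section 1.4)
- 460 women with a 4–10% increase by 6 months (Group B)
- 46 later cases in the under-4% group (section 2.0)
- 30–40% incidence, with 80–90% of it arising within two years (section 1.1)

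| Reading | Events | Variables at 30 each | Variables at 10 each |
|---|---|---|---|
| Early cases kept | 350 | 11.7 | 35.0 |
| All 210 excluded, all among the 350 | 350 − 210 = 140 | 4.7 | 14.0 |
| Same, 1100 women, no loss | 385 − 231 = 154 | 5.1 | 15.4 |
| Same, 18-month incidence assumed 30% to 40% | 90 to 190 | 3.0 to 6.3 | 9 to 19 |
| 5% early swelling in place of 21% | 350 − 50 = 300 | 10.0 | 30.0 |
| Section 1.4 progression figure | 0.60 × 460 + 46 = 322 | 10.7 | 32.2 |
| 210 excluded, all later events added (350 assumed to be 90% or 80% of the eventual total) | 389 − 210 = 179, or 438 − 210 = 228 | 6.0 to 7.6 | 17.9 to 22.8 |
| Early cases kept, all later events added | 389 to 438 | 13.0 to 14.6 | 38.9 to 43.8 |

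The third column is also the number of events per variable if 30 variables are used. It ranges from 3.0 to 14.6 and never approaches 30.

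The inputs do not fully agree with one another. For example, 322 later events plus 210 early ones would make 532, well above 350. The rows are alternative readings and cannot be added together.

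**4. What this means for weak relationships.** The protocol gives no significance level, effect size or power for this analysis, so this step is illustrative. Assume a two-sided 5% level, 80% power, a factor splitting the women 50:50, and no adjustment for other covariates. The detectable hazard ratio is exp(2.80 / √(0.25 × events)), which gives 1.61 with 140 events, 1.38 with 300 and 1.35 with 350.

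**The case against.** The strongest reply is that 140 is only one reading. Much of that reply stands.

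- **Overlap.** The subtraction assumes that all 210 early cases are among the 350. The 350 is a status at the 18-month visit, and the Group C text says that some swelling improves. If some early cases are negative at 18 months, more than 140 first events occur later.
- **Size of the exclusion.** Analysis 4 excludes lymphoedema arising before 6 months, while Group C counts women with swelling by 6 months, including any first seen at that visit. Sections 1.4 and 7 also require more than 10% on at least two occasions. So 210 may be too many.
- **The alternative factor.** If early cases are kept, 350 events give 11.7 per variable for 30 variables, within the quoted range of 10 to 30.
- **Follow-up.** The analysis runs 18 months after the last entry, so early recruits add later events.

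Two stronger readings are tempting, and the protocol does not support either. A reader might infer that the expectation of few exclusions is a miscount of the 210. It refers to women treated before 6 months, a narrower group, so the fault is that two rules differ. A reader might also infer that the 6-month exclusion is needless throughout. It is not, because the candidates include questionnaire, perometer and BEA values up to 6 months, and such predictors need a 6-month starting point.

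None of these points rescues the quoted sentence. Even the most favourable row reaches fewer than 15 events per variable, against the 30 that the text attaches to weaker relationships.

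**Conclusion.** The stated count is wrong in kind: it applies the rule to women when it should apply to events. Two figures bracket the main case by 18 months per 1000 women. With early cases kept there are about 350 events, or about 12 variables at 30 each and 35 at 10 each. With all 210 excluded and all among the 350, there are about 140 events, or 5 to 14 variables. Thirty variables meet the minimum of 10 each only if most early cases stay in. No reading tested supports 30 variables at 30 each.

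The conclusion rests on reading the rule as events per variable, which is standard for a Cox model with censoring but is not stated in the protocol. It would be too strong to say that the plan leaves 140 events without qualification, since the protocol does not settle which early cases are excluded.

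The issue concerns a secondary objective and changes neither the primary endpoint nor the number of patients. It should be fixed, but it is not critical.

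**What to change.** 1. Replace the sentence with an event-based count. Give the expected events under the chosen exclusion rule and the number of parameters they support at 10 and at 30 events each.
2. Limit the candidate parameters to that number, for example by entering questionnaire total scores and not individual items.
3. Reconcile the three statements on early cases in section 5. A sound way is to model baseline factors in all women from surgery (about 350 events by 18 months), and to use the 6-month exclusion only for models with predictors measured up to 6 months (about 140 events on the strictest reading).
4. State whether the exclusion applies to all lymphoedema before 6 months or only to women treated by then, and give the expected number for that definition.

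Shrinkage, internal validation and the method of variable selection can be left to the SAP; the point does not depend on them. The cost is a less favourable stated variable count and a little more analysis work. No more patients or visits are needed.

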2.0 TRIAL DESIGN

1100 women undergoing ANC for breast cancer in 9 centres across the UK will be approached to undergo baseline (pre-operative) and subsequent BEA monitoring, along with perometer arm measurements (see flow diagram). A comparison of the sensitivity and specificity of BEA versus perometer measurement will be made firstly in women who develop arm swelling >10% by 6 months (estimated at 231/1100 (21%) of the initial group). Percentages are estimated from ALMANAC Trial (see Annex 4d). Secondly women with an arm volume increase 4-8.9% at 1, 3, 6 months where effectively the BEA 6 months readings will be compared with final 18 month perometer scores to assess the prediction of lymphoedema at 18 months by BEA. Thirdly, women with a <4% Perometer arm volume increase up to 6 months (estimated n=363/1100 with estimated lymphoedema at 18 months of 46 (14% of 264)) will be used to determine the sensitivity and

specificity of BEA 6 month measures compared to the perometer 6 month measurement in predicting the 18 month outcome.

We originally estimated we would need to screen over 1000 patients to enrol sufficient women into the PLACE Trial using perometer measurements, we will determine if BEA has a >80% sensitive and a >80% specific accuracy and currently the specificity of arm swelling measured by perometer is 87% specific for subsequent lymphoedema at 18 months with a sensitivity of 54% (assessed from ALMANAC trial data). We will recruit 1100 women before ANC into the five year study to allow for 10% drop-out over the course of the study.

The Perometer sensitivity is reported as 85% +/-3.6% (95% CI 81.4% to 88.6%) and we will be able to detect a greater or equal to 7% improvement in sensitivity with BEA to 92+/-2.5% (95%CI: 89.5-94.5%) and the Perometer specificity is 55% +1-4.1% (95% CI 50.9% to 59.1%) thus we will be able to detect a >9% improvement in specificity with BEA to 64%+/-3.9% (95%CI:60.1 to 67.9%) with this sample size, since the confidence intervals do not overlap.

Gold standard at 18 months	Test P+	Test P-	Total
	+168[contact]
	-168[contact]
Total	336[contact]

sensitivity = 307/352 = 87%
 specificity = 284/523 = 54%

Arm volume measurement at 1 month will not be used to implement treatment outside of the trial. In women who develop lymphoedema >10% at 3 months, sleeves will be applied and the 3 month BEA value compared to the perometer used in the analysis. For all others, the 6 month value will be used.

[figure not shown]

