5 STATISTICAL ANALYSIS

Analysis 1 and 2 will directly compare BEA and perometer assessment at a given time point (6 and 18 months). The reported concordance/correlation in small series is 0.93¹³⁴¹. Thus, even if a sleeve has been applied in patients before 6 months' measurements and the arm circumference has been reduced, the reduction in fluid in the arm should have reduced both the perometer and BEA scores concomitantly.

Sample Size Calculation

We estimate 1100 women are needed for screening by perometer to recruit 270 women to the PLACE trial and this sample size of 1100 (derived from having approached 1500 women to take part in the study) allows us to assess equivalence for sensitivity and specificity for BEA compared to perometer measurement with tight confidence intervals. Previous reported correlation between the techniques is very high¹¹⁵, and this sample size allows us to have a 95% Confidence Interval (CI) around our sensitivity and specificity estimates such that they are $\pm 5\%$ or less. Thus if perometer and BEA are equivalent in sensitivity and specificity to within 5% of each other, we would expect that the BEA would become the preferred option as it would be mobile, non-invasive and simpler to use in any outpatient setting compared to a fixed, large instrument, such as the perometer. There will be less patients with lymphoedema at 6 months but nonetheless if BEA sensitivity is 95% of the perometer sensitivity, we can demonstrate this with a 95% CI of 91.42% to 97.49%. If the BEA sensitivity rate was as low as 90%, we would have a 95% CI of 85.12% to 93.49%. All subsequent analyses will use sample sizes based on larger numbers as there will be more lymphoedema events at 18 months and again at 36 months but their confidence intervals are within $\pm 5\%$. We have used the exact method for calculating confidence intervals for a binomial proportion (Documenta Geigy Scientific tables page 185 equation 769); the actual calculation was done using the www.measuringusability.com/wald.htm website calculator.

The sample will allow us to measure accurately, inter- and intra-technique variability at different time points.

Analyses 1 to 3 will assess whether BEA can be used instead of perometer in defining lymphoedema status. The second group of analyses is to look for any variables collected at operation or in the first 6 months post operation that singly or in combination can be used to predict lymphoedema status at or beyond 18 months.

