Analysis 1

Sensitivity and specificity analysis of the BEA assessment (lymphoedema or not) against the 'gold standard' perometer assessment (lymphoedema or not) using data available by 6 months.

Analysis 2

Analysis of the sensitivity and specificity of the 18 month BEA assessment status (lymphoedema or not) against the 'gold standard' 18 month perometer assessment status (lymphoedema or not) using all data available at 18 months.

Analysis 3

Assessment of the relationship between perometer measurement and BEA measurement.

Analysis 4

Cox regression multivariate analysis of the time to Lymphoedema (as defined by perometer) to find out which combination of variables gives the best prediction of this complication.

Analysis details:

Analysis 1: Sensitivity and specificity analysis of the BEA assessment (lymphoedema or not) against the 'gold standard' perometer assessment (lymphoedema or not) using data available by 6 months. Can BEA be used instead of perometer in predicting lymphoedema status?

All cases with a 6 month BEA and perometer measurement will be used. This is acceptable even if some cases are treated as what we are asking is do cases measured at the same time (and therefore under the same circumstances whatever they are) agree in their assessment of lymphoedema status.

The two methods will not agree on their actual scores as perometer measurements are in percentage differences and BEA measures are ratios. However we will assess the relationship between all the pairs of values using statistical techniques recommended by Bland and Altman for assessing agreement between methods of measurements with multiple observations per individual^{36,311} (see also analysis 3).

With 1100 cases consented to having measurements taken and followed-up, we would expect 231 to have developed lymphoedema (positive) using perometer assessment and 869 to be negative at 6 months. If we accept that BEA status has at least 95% sensitivity and 95% specificity against the perometer status then the 95% CI for sensitivity based on 231 cases is 91.42% to 97.49% and for specificity based on 869 cases is 93.31% to 96.47% (CI's calculated by 'exact' method). Consequently if sensitivity is <91 % or specificity is <93% we can conclude that the true BEA rates are not as high as 95%. This analysis can be done 6 months after the last case has their 6 months measurements taken. The perometer is deemed to be the gold standard.

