All percentages for the 3 groups (A-C) are estimated from ALMANAC Trial data (see Annex 4d). None of the analyses outlined will use cases where a treatment for lymphoedema has been given prior to 6 months as explained above. A "treatment paradox" will not affect analyses 1 to 3 and treatment will be a variable in analysis. Potentially, the predictive value of a measurement at 6 months by perometry of the arm may be altered by treatment when assessing lymphoedema at 18 or 36 months. We do not believe this will occur for the majority of patients but in any case we will take account of this in the Cox multivariate regression analysis based on perometer measurements at 18 and 36 months and by looking at variables which include treatment with a compression sleeve. As we indicated in the flow diagram of this study, 3 possibilities may arise:

- Group A: Women in whom the arm volume increase is less than 4% at all time points up to 6 months (approximately 33% of the population; 330 individuals). None of these patients will undergo treatment within the first 6 months and therefore the measurement at 6 months will not be subject to "treatment paradox" and should they subsequently develop lymphoedema before 18 months, they will be registered as having developed the lymphoedema event in a time-dependant manner for the multivariate analysis and subsequent treatment will not affect this analysis.
- Group B: Women who will have developed a 4-10% arm volume increase by 6 months (estimated as 46% of the total group; 460 patients). Around 135 women from this group (with a 4-8.9% volume increase) will go into the PLACE trial and have a sleeve applied and a similar number will go into the PLACE trial and will not have an arm sleeve applied.

Thus, in this group there will be 325 patients (460 minus 135) who are not treated until they develop lymphoedema and will not have a "treatment paradox" for the same reason as previously described. Out of the 135 cases allocated to the sleeve arm within the PLACE trial, who are chosen at random, we will use their data in a multivariate analysis as we will incorporate it as a factor, sleeve versus no sleeve in building the model.

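### The protocol gives three incompatible rules for women sleeved before 6 months, so the population for BEA sensitivity in Analyses 1 and 2 is not fixed

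*Protocol*

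**What the plan says.** All the text is in the current protocol.

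- **Section 5, Analysis 1:** "All cases with a 6 month BEA and perometer measurement will be used. This is acceptable even if some cases are treated". The opening of Section 5 gives the reason for Analyses 1 and 2: "even if a sleeve has been applied in patients before 6 months", the fall in fluid should lower both scores together. Analysis 2 is then said to follow the logic and procedures of Analysis 1 at 18 months.
- **Section 5, before Groups A to C:** "None of the analyses outlined will use cases where a treatment for lymphoedema has been given prior to 6 months as explained above". The next sentence says that the treatment paradox does not affect Analyses 1 to 3.
- **Section 2.0, below the sensitivity and specificity table:** "In women who develop lymphoedema >10% at 3 months, sleeves will be applied and the 3 month BEA value compared to the perometer used". Everyone else contributes the 6-month value.
- **Section 5, Group C:** 3-month perometer readings are compared with 3-month BEA. Women treated before 6 months are left out of the multivariate analysis, and few such exclusions are expected.
- **Section 5, Group B:** for the roughly 135 women in the PLACE sleeve arm, "we will use their data in a multivariate analysis as we will incorporate it as a factor, sleeve versus no sleeve".
- **Section 5, Analysis 4:** the exclusion is of women who develop lymphoedema before 6 months, with sleeve use as a model factor. A later sentence allows an early-treatment or early-status factor instead, so that all the information is used.

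**The concern.** A woman above 10% and sleeved after her 3-month visit enters Analysis 1 with her 6-month pair, with her 3-month pair, or not at all, depending on the sentence followed. Her perometer status can change too. Section 5 accepts that a sleeve may reduce the swelling, so she may be positive at 3 months and negative at 6.

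This touches sensitivity more than specificity. Outside PLACE, treatment follows perometer readings above 10%, so women treated early belong to the perometer-positive group. That group is the sensitivity denominator, and Analysis 1 attaches a decision reading to its expected size of 231: an observed sensitivity below 91% is taken to show that the true rate is under 95%. If the population stays open, it could be chosen after BEA's sensitivity has been seen. Dropping treated women may also leave positives who are on average nearer the 10% threshold, where two methods disagree most often.

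**Working it through.** **1. The rules side by side**, for a woman above 10% at 3 months, sleeved, and measured by both methods at 3 and 6 months:

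| Source | What she contributes to Analysis 1 |
|---|---|
| Section 5, Analysis 1 | 6-month pair |
| Section 5, sentence before Groups A to C | nothing |
| Section 2.0 | 3-month pair |

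**2. The plan's own figures.** Expected positives: 0.21 × 1100 = 231; negatives: 1100 − 231 = 869. The exact (Clopper-Pearson) limits for x positives out of n are the 2.5% quantile of Beta(x, n − x + 1) and the 97.5% quantile of Beta(x + 1, n − x). With n = 231 and x = 0.95n this gives 91.34 to 97.43, against the stated 91.42 to 97.49: agreement within 0.1 point. Analysis 2 reproduces exactly: 333/350 gives 92.34 to 97.15, and 618/650 gives 93.12 to 96.61.

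**3. Precision if treated positives are excluded.** The protocol does not say how many of the 231 are treated before 6 months, so the share is an assumption.

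| Share excluded | Positives left | Exact 95% CI at exactly 95% | Nearest whole count |
|---|---|---|---|
| 0% | 231 | 91.3 to 97.4 | – |
| 10% | 208 | 91.1 to 97.5 | – |
| 25% | 173 | 90.6 to 97.7 | 164/173: 90.4 to 97.6 |
| 50% | 116 | 89.3 to 98.2 | 110/116: 89.1 to 98.1 |
| 75% | 58 | 85.9 to 99.0 | 55/58: 85.6 to 98.9 |

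At exactly 95%, the lower limit first falls more than 5 points below 95% at n = 141 (89.99), which is 1 − 141/231 = 39% excluded. The half-width first exceeds 5 points at n = 93 (88.4 to 98.4), which is 1 − 93/231 = 60% excluded.

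**4. Analysis 2, worst case.** Suppose every early positive were treated, excluded, and would have been positive at 18 months. Then 350 − 210 = 140 positives remain (90.0 to 98.0), or 350 − 231 = 119 (89.4 to 98.2).

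**5. Direction of bias.** Assume bivariate normal scores, correlation 0.93 (the figure in Section 5), and both methods cut at 21% prevalence. Simulated sensitivity (4 million draws) is 79.5% with all positives kept. This model illustrates a shift; it does not predict BEA sensitivity. Exclusion is triggered by an earlier reading, whose correlation with the 6-month value I assume to be 0.3 to 0.7.

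| Share of positives excluded | Selected on earlier reading | Most swollen at 6 months removed |
|---|---|---|
| 10% | 78 to 79% | 77% |
| 25% | 77 to 79% | 73% |
| 50% | 74 to 78% | 64% |
| 75% | 72 to 77% | 53% |

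The middle column matches the stated rule. The right-hand column is an extreme.

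**The case against.** The best defence is that the blanket sentence is merely over-broad. Its reference to an earlier explanation fits Analysis 4, where exclusion is argued for; the sentence after it sets Analyses 1 to 3 apart; and Group C limits exclusion to the multivariate analysis and expects few. This is probably what was meant, but the words cover every analysis outlined. Reading them as Analysis 4 only still leaves Section 2.0 and Analysis 1 in conflict over which pair an early-sleeved woman contributes.

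The objection does stand against stronger readings:

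- A reader might infer that the 231 positives disappear under the exclusion. They do not. Section 3.4 starts treatment on readings above 10% on two occasions, and a woman first above 10% at the 6-month visit has not been treated before it, so she stays in under every rule.
- A reader might take 231 to support both analyses. It supports Analysis 1 only; Analysis 2 rests on 350 and 650.
- A reader might expect sensitivity to collapse. The 64% and 53% figures require removing women by the 6-month value itself, which no rule does.
- A reader might suppose that most women sleeved early are positives. The only sleeve count given is about 135 PLACE women, who enter at 4 to 8.9%; how many of them start before 6 months is not stated.

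**Conclusion.** The contradiction is real and should be corrected. Analysis 1 has three candidate populations, and Analysis 2 has two: all 18-month pairs, or those pairs without women treated before 6 months. The choice changes who enters the sensitivity denominator.

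The likely size is modest. If few positives are treated early (10%, say), the interval hardly moves. At 25% the lower limit drops by about one point from the stated 91.42, and the aim of 5 points either side is lost only at about 40% (lower limit) to 60% (half-width). Downward bias in BEA sensitivity is possible: about 1 to 5 points in the illustrative model for 25 to 50% excluded on an earlier reading. These sizes rest on assumed shares and correlations. The conflict between the rules does not.

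Analysis 4 is also unsettled. One passage excludes on developing lymphoedema before 6 months, another on having been treated, and the PLACE sleeve arm is kept although the blanket sentence, read broadly, would remove those sleeved before 6 months.

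**What to change.** - **Exclusion sentence:** limit it to Analysis 4.
- **Analysis 1:** state one rule and use it in Section 2.0, Analysis 1 and the Group A to C text. For example, each woman contributes her last same-visit BEA and perometer pair before any sleeve, up to 6 months. Repeat on all 6-month pairs as a sensitivity analysis.
- **Analyses 2 and 3:** state that Analysis 2 uses all 18-month pairs and Analysis 3 all available pairs, regardless of earlier treatment.
- **Analysis 4:** reconcile the Analysis 4, Group B and Group C text on whether women who developed lymphoedema, or who were treated, before 6 months are excluded, given that the PLACE sleeve arm is retained.

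The cost is wording and one extra run. The small downside is that 3- and 6-month pairs are pooled in Analysis 1. No measurement or patient's care changes.
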